10.2 Potential Risk from Intervention

The following sections describe potential risks associated with the remote-support weight loss intervention along with procedures to minimize risk.

10.2.1 Physical Activity

During the screening process, we will exclude persons with uncontrolled medical illnesses for which physical activity would be contraindicated.

In order to protect the participants' safety, we will continuously reinforce our recommendation to engage in moderate-intensity physical activity. We will also recommend a safety evaluation by their Primary Care Physician (PCP) for those participants who wish to progress to vigorous physical activity. Still, it is important to acknowledge the participant autonomy. We can recommend that participants follow safety advice but cannot force them to do so.

10.2.2 Nutrient Intake

Calorie restriction can theoretically lead to inadequate nutrition or excessive, rapid weight loss (>10% weight loss within 4 weeks or a total weight loss of >25%). If a participant loses >10% weight within 4 weeks, the team will review the patient's food diary to ensure that they are not over restricting their calories (e.g., <1000 daily). If people achieve more than a 25% weight loss, then the team will evaluate for cancer (recurrence in our population), eating disorders, and hyperthyroidism. To minimize these risks, participants are encouraged to eat a variety of foods from all food groups and to maintain an adequate calorie level. If nutritional deficiency is suspected and unresponsive to advice from the interventionist, the intervention will be suspended and the participant will be referred to her PCP. Participants will be advised that marked and sustained caloric restriction can have serious health risks, e.g., malnutrition.

10.2.3 Hypoglycemia

For patients who may be susceptible to hypoglycemia due to use of anti-diabetic medications, weight loss interventions have the potential to increase the risk of hypoglycemia, especially during the time when diet and/or physical activity interventions are implemented. For this reason we will exclude patients who take insulin or sulfonylureas. We will allow patients to enroll if their diabetes is controlled on metformin. If participants have a drop in HbA1c to <6.5 or if they require a change in diabetic medications during this study, they will be overseen by the Protocol Chair and/or co-investigator and the PCP will be notified of these changes.

10.2.4 Symptomatic Hypotension

For patients who may be susceptible to hypotension because they are using medications that lower blood pressure, weight-loss interventions have the potential to increase the risk of hypotension. Participants are educated about symptoms of hypotension and urged to contact the research nurse or PCP if they have symptoms suggestive of hypotension. In addition, staff contact will notify the Protocol Chairof participants who develop symptomatic hypotension while on anti-hypertensive medications. Changes in blood pressure regimen may be performed by the Protocol Chair and/or co-investigators and the participant's PCP will be notified.

10.2.5 Cardiovascular Events

All participants with cardiovascular disease (CVD) require approval from their PCP and Protocol Chair prior to enrolling. If this medical condition is not felt to be stable, patients will be excluded from this study. In addition, participants are educated about CVD symptoms and urged to contact their PCP if they have a change in their CVD symptoms. Overall CVD management remains under the control of the participant's PCP.

10.2.6 Symptoms Related to Contrave

The pharmacotherapy could lead to adverse effects: nausea (NB32 29%, NB16 27%). Headache (NB32 13%, NB16 27%), constipation (NB32 15%, NB16 15%), dizziness (NB32 9%, NB16 7%), insomnia (NB32 7%, NB16 6%), vomiting (NB32 9%, NB16 6%), and dry mouth (NB32 7%, NB16 7%)⁹⁵. Adverse events were most frequently gastrointestinal in nature. The most common of these, nausea was generally mild to moderate in intensity, transient, and did not result in discontinuation for most participants who reported it. Nausea was typically first reported during dose escalation in the experimental groups; the rate of onset seemed to plateau shortly after reaching full dose and then was similar to the rate reported in the placebo group. The most frequent adverse events leading to discontinuation before week 26 included nausea (10.5%); anxiety (3.3%); and headache, hypertension, insomnia and palpitations (1.3% each)⁹⁸. While attrition across all phase III studies of Contrave ranged from 42% to 50%, only 24% of those taking Contrave withdrew due to adverse events (vs 12% taking placebo)⁹³.

Participants will be educated about the side effect profile and urged to contact the research nurse if they have symptoms. Depending on the severity of the side effect, the dosage may be decreased or discontinued entirely. Patients whom are discontinued on the pharmacotherapy will continue the study with BWL alone. Changes in overall management of hypertension remain under the control of the PI.

10.2.6 Survey fatigue

Minimal risks associated with completing the questionnaires include subject fatigue and the possibility of minor psychological distress. Participants are instructed that they may refuse to answer any questions.

10.3 Definitions

• Adverse event (AE): Any undesirable sign, symptom or medical condition occurring after starting therapy even if the event is not considered to be related to the study. An undesirable medical condition can be symptoms (e.g., nausea, chest pain), signs (e.g.,

tachycardia) or the abnormal results of an investigation (e.g., laboratory findings, biopsies).

Medical conditions/diseases present before starting study treatment are only considered adverse events if they worsen after starting study treatment (any procedures specified in the protocol). Adverse events occurring before starting study treatment but after signing the informed consent form will be recorded. Abnormal laboratory values or test results constitute adverse events only if they induce clinical signs or symptoms or require therapy.

Serious adverse event or reaction: Any untoward medical occurrence secondary to therapy that: results in death, is immediately life-threatening, requires inpatient hospitalization or prolongation of existing hospitalization, results in persistent or significant disability / incapacity, or is an important medical event that may jeopardize the subject or may require medical intervention to prevent one of the outcomes listed above.

The definition of serious adverse event (experience) also includes *important medical* event. Medical and scientific judgment should be exercised in deciding whether expedited reporting is appropriate in other situations, such as important medical events that may not be immediately life-threatening or result in death or hospitalization but may jeopardize the patient or may require intervention to prevent one of the other outcomes listed in the definition above. These should also usually be considered serious.

A hospitalization planned before the start of the study agent(s) and/or for a preexisting condition that has not worsened does not constitute a serious adverse event (e.g., elective hospitalization for breast reconstruction of the ipsilateral breast). A hospitalization for a social reason in the absence of an adverse event also does not meet the criteria for a serious adverse event.

- Unexpected adverse event: An adverse event, which varies in nature, intensity or frequency from information on the investigational intervention provided in the Investigator's Brochure, package insert or safety reports. Any adverse event that is not included in the informed consent is considered "unexpected".
- Expected (known) adverse event: An adverse event, which has been reported in the Investigator's Brochure. An adverse event is considered "expected", only if it is included in the informed consent document as a risk.

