10. ADVERSE EVENTS

10.1 General

This study will use the descriptions and grading scales found in the revised National Cancer Institute Common Terminology Criteria for Adverse Events (CTCAE) Version 4.0 for adverse event reporting that can be found at http://ctep.cancer.gov/reporting/ctc.html. Information about all related adverse events, whether volunteered by the subject, discovered by investigator questioning, or detected through physical examination, laboratory test or other means, will be collected, recorded, and followed as appropriate.

It should be noted that only those adverse events believed to be related to the weight loss intervention will be collected and tabulated during the course of the study. The side effects with

the weight loss intervention we might encounter include anxiety and frustration. While this program is not designed to cause radical weight loss, in the unlikely event this were to occur radical weight loss can cause several medical implications including dehydration, malnutrition, electrolyte disturbances, headaches, nausea, and tachycardia. Blood samples for research correlated will require intravenous access which may include discomfort, bruising and, rarely, infection, syncope, or significant bleeding; these will be collected at planned standard of care testing, whenever possible.

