10.4 Relationship

The relationship of all adverse events and serious adverse events to study medication will be assessed by an investigator and assigned as follows:

- Definitely: An adverse event which has a timely relationship to the administration of the investigational drug/agent, follows a known pattern of response, for which no alternative cause is present.
- Probably: An adverse event, which has a timely relationship to the administration of the investigational drug/agent, follows a known pattern of response, but for which a potential alternative cause may be present.

- Possibly: An adverse event, which has a timely relationship to the administration of the investigational drug/agent, follows no known pattern of response, but a potential alternative cause does not exist.
- Unlikely: An adverse event which does not have a timely relationship to the administration of the investigational drug/agent, follows no known pattern of response, does not reappear or worsen after re-administration of the investigational drug/agent (if applicable), and for which there is evidence that it is related to a cause other than the investigational drug/agent.
- Unrelated: An adverse event, for which there is evidence that it is definitely related to a cause other than the investigational drug/agent. In general, there is no timely relationship to the administration of the investigational drug/agent, or if there is a timely relationship, the event does not follow a known pattern of response, and there is an alternative cause

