10.5.2 Serious Adverse Events

All serious adverse events, regardless of causality to intervention, will be reported to the PI.

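### Section 10.3 makes cause part of the definition of a serious adverse event, while 10.5.2 expects serious events to reach the PI whatever their cause

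*Combined protocol and SAP*

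**What the plan says.** Four parts of section 10 of the combined protocol and SAP bear on this.

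- **10.3 Definitions, serious event.** The entry reads "Any untoward medical occurrence secondary to therapy that: results in death, is immediately life-threatening" and goes on to the other usual seriousness criteria. One entry serves for both event and reaction.
- **10.3 Definitions, adverse event.** This entry carries no causal condition. It applies "even if the event is not considered to be related to the study".
- **10.4 Relationship.** "The relationship of all adverse events and serious adverse events to study medication will be assessed by an investigator", on a five-step scale whose lowest grade is "An adverse event, for which there is evidence that it is definitely related to a cause other than the investigational drug/agent".
- **10.5.2 Serious Adverse Events.** "All serious adverse events, regardless of causality to intervention, will be reported to the PI".

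Three further provisions decide what happens to an event that is not classed as serious. Section 10.5.1 has every AE entered on the case report forms. Section 10.5.3 has AEs and SAEs reported to the IRB under institutional standards. Section 10.1 pulls the other way, stating that "only those adverse events believed to be related to the weight loss intervention will be collected and tabulated during the course of the study".

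**The concern.** An SAE definition should turn on seriousness alone, with cause judged separately. Here the definition applies a causal test before the reporting rule is reached. A reporting rule that disregards cause cannot bring back an event that the definition has already excluded on cause. Staff who work from the definition and staff who work from the reporting rule will treat the same unrelated hospitalisation differently.

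Two things are at stake: whether the event carries the serious label, and hence appears in any SAE count, and whether the PI is notified under 10.5.2. That notice has some weight because other oversight is light. Section 11.3 leaves monitoring to project personnel, with a limited review of 10% of subjects in the last year and an annual committee review. The committee in 11.4 is convened for disclosure questions, not for safety. The trial is single-arm, so no control group would show up an under-count.

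**Working it through.** The plan states no figure to reproduce, and no alpha, power or sample size enters. The check is to take three kinds of serious occurrence through the provisions as written.

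| Occurrence | AE under 10.3? | SAE under 10.3, read literally? | 10.4 grade (relation to study medication) | 10.5.2 notice to PI |
|---|---|---|---|---|
| A. Hospitalisation attributed to Contrave | Yes | Yes | One of the upper grades | Yes |
| B. Hospitalisation attributed to exercise or calorie restriction in a woman not on Contrave | Yes | Yes, because the behavioural programme is part of the therapy | Unrelated | Yes |
| C. Unplanned hospitalisation or death judged unrelated to both the programme and the drug | Yes | **No**, the causal condition fails | Unrelated, as an AE | **Not triggered**, although 10.5.2 says cause is irrelevant |

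**Where the conflict lies.** Rows A and B are consistent. Row C is the problem, and it sets 10.3 against 10.5.2. If the causal condition stands, the clause in 10.5.2 that disregards cause has almost nothing left to act on.

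**What happens to a row C event.** It remains an AE, because that definition ignores cause. It is entered on the case report form (10.5.1), graded (10.4) and within IRB reporting (10.5.3). Only 10.1 would keep it out of collection and tabulation, and 10.1 conflicts with 10.5.1 on exactly that.

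**Direction.** Let R be the number of serious occurrences judged due to therapy and U the number judged not due to therapy.

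- Count if cause is ignored: R + U.
- Count under 10.3 read literally: R.
- Difference: U, which is at least 0.

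The literal count is therefore equal or lower, never higher.

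**Scale per event.** The plan expects 55 women, about 30 of them in SLOW-BWL. One woman with a single row C event moves the SAE proportion by 1/55 = 1.8 percentage points of all enrolled, or by 1/30 = 3.3 points if she is in SLOW-BWL and that group is the denominator. These are unit conversions, not estimates of how many such events will occur.

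**The case against.** The best defence is that the intent can be recovered. The heading of the definition merges two terms, event and reaction, and the causal phrase suits only the second. The same section adds that "A hospitalization for a social reason in the absence of an adverse event also does not meet the criteria for a serious adverse event", and it also excludes hospitalisations that were planned or were for an unworsened pre-existing condition. These exclusions would be largely redundant if cause were already required. Section 10.5.2 is explicit, and many sites would follow it. In addition, the weekly survey in Appendix C sends new symptoms in months 3-6 to the PI, which gives some events another route. All of this is fair, and it makes a drafting slip the likely explanation. But no sentence says that 10.5.2 overrides the definition, and if that is the intent, the correction only makes 10.3 say so.

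Three stronger readings are tempting, and the documents do not support them.

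- **That an SAE graded Unrelated cannot exist.** Row B shows that it can. Section 10.4 grades relation to the study medication only, while therapy in 10.3 also takes in the behavioural programme. Section 10.4 is therefore not in direct contradiction with the definition.
- **That an unrelated serious event escapes all further scrutiny.** Sections 10.4, 10.5.1 and 10.5.3 still reach it as an AE. What is lost is the serious label and the 10.5.2 notice.
- **That a fall in the SAE rate can be quantified, or that the SAE count is the main safety summary.** The documents give neither an SAE rate nor a share judged due to therapy. Section 13.2 promises only a descriptive summary of safety measurements.

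**Conclusion.** The inconsistency between 10.3 and 10.5.2 is real and should be corrected. Read literally, the definition denies the serious label and the PI notice to a death, life-threatening event or hospitalisation judged unrelated to the intervention, and 10.5.2 plainly means such events to be reported.

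The direction is certain: the SAE count stays the same or falls. The size cannot be given, because it depends on how many serious occurrences are judged unrelated and on which section staff follow. The primary endpoint, the Simon two-stage boundaries and the futility rule are untouched.

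The conclusion rests on reading the definition as written. Text between 10.5.3 and section 11 was not available for checking, so a clarification there cannot be excluded.

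**What to change.** 1. In 10.3, delete the words *secondary to therapy* from the SAE entry, so that an SAE is any untoward medical occurrence meeting a seriousness criterion, whatever the suspected cause.
2. Keep causality as the separate 10.4 grade, and leave 10.5.2 as written.
3. State in 10.1 that its restriction to related events does not apply to SAEs, and tabulate SAEs overall and by relationship. Without this step the first change would not deliver the table, because 10.1 would still limit tabulation to related events. Since 10.4 grades relation to study medication, the table should be labelled accordingly.

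The cost is a short protocol amendment, a few more SAE forms and possibly a higher reported SAE count. Treatment, sample size and the efficacy analysis do not change.

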10.4 Relationship

The relationship of all adverse events and serious adverse events to study medication will be assessed by an investigator and assigned as follows:

- Definitely: An adverse event which has a timely relationship to the administration of the investigational drug/agent, follows a known pattern of response, for which no alternative cause is present.
- Probably: An adverse event, which has a timely relationship to the administration of the investigational drug/agent, follows a known pattern of response, but for which a potential alternative cause may be present.

- Possibly: An adverse event, which has a timely relationship to the administration of the investigational drug/agent, follows no known pattern of response, but a potential alternative cause does not exist.
- Unlikely: An adverse event which does not have a timely relationship to the administration of the investigational drug/agent, follows no known pattern of response, does not reappear or worsen after re-administration of the investigational drug/agent (if applicable), and for which there is evidence that it is related to a cause other than the investigational drug/agent.
- Unrelated: An adverse event, for which there is evidence that it is definitely related to a cause other than the investigational drug/agent. In general, there is no timely relationship to the administration of the investigational drug/agent, or if there is a timely relationship, the event does not follow a known pattern of response, and there is an alternative cause

10.5 Reporting Procedures

10.5.1 General

All adverse events will be captured on the appropriate study-specific case report forms (CRFs) through CRMS and REDCap. The Coordinating Center may also periodically request that deidentified AE logs and deviation logs be submitted via encrypted email, such as for annual continuing review.

10.5.2 Serious Adverse Events

All serious adverse events, regardless of causality to intervention, will be reported to the PI.

10.5.3 Institutional Review Board (IRB)

All adverse events and serious adverse events will be reported to the IRB per current institutional standards. If an adverse event requires modification of the informed consent, these modifications will be provided to the IRB with the report of the adverse event. If an adverse event requires

modification to the study protocol, these modifications will be provided to the IRB as soon as is possible.

11. DATA AND SAFETY MONITORING

11.1 Data management

Participant information relevant to the study will be recorded on a paper case report forms customized for this study. Only the PI and authorized staff, according to the list of Authorized Study Personnel are entitled to make entries on these forms. Case report forms will identify patients by initials and number only. Personal patient data will be kept confidential. The PI will keep in his/her file a Patient Identification and Enrollment List. Data generated from the case report forms will be transferred to a study database on REDCap

(https://www.jhubc.org/REDCap/) - a secure, web-based application for building and managing online surveys and databases. All information obtained during the study will be regarded as confidential. All study data will be reviewed for completeness and accuracy by the coordinating center. The study data will also be periodically reviewed by the SKCCC Clinical Research Office (CRO).

11.2 Meetings

Scheduled meetings will take place as needed with the medical oncology co-investigators and study personnel. In addition, separate meetings will be scheduled and include the protocol PI, study coordinator(s), data manager(s), collaborators, and biostatistician involved with the conduct of the protocol. During these meetings matters related to the following will be discussed: safety of protocol participants, validity and integrity of the data, enrollment rate relative to

expectation, characteristics of participants, retention of participants, adherence to protocol (potential or real protocol violations), data completeness, and progress of data for objectives.

11.3 Monitoring

This is a project which does not include an investigational drug, agent, or device. Thus, the monitoring will be done by the project personnel.

The project may be periodically monitored by the SKCCC Clinical Research Review Committee (responsible for scientific oversight of studies) and the SKCCC CRO.

This is a non-therapeutic interventional trial, which is DSMP low risk study under the SKCCC Data Safety Monitoring Plan version 6.0 (dated 2/21/2019). The CRO QA Group will perform a regulatory and limited subject review during the last year of study with random selection of 10% of all subjects. All trial monitoring and reporting will be reviewed annually by the SKCCC Safety Monitoring Committee.

